13.3.2. Assessment Windows for PK Concentration Data

PK data will be presented in data listings according to planned nominal visits (i.e. as collected in the eCRF), without additional assignment to assessment windows.

13.4. Appendix 4: Study Phases and Treatment Emergent Adverse Events

13.4.1. Study Phases

AEs will be assigned to study phases as defined in Table 6. Laboratory data (efficacy, safety, and virology), HIV associated Conditions, health outcomes assessments, vital signs, and ECGs will be assigned to study phases as defined in Table 7.

Assessments/events are assigned to study phases sequentially, starting from the top of each table.

Table 6 Study Phases for AEs

Study Phase	Definition
Screen	Date < Intervention Phase Treatment Start Date
Intervention	
For subjects continuing into the Extension Phase: Intervention Phase Treatment Start Date \leq Date < Date of Nominal Month 13 Visit
 
For subjects not continuing into the Extension Phase: Intervention Phase Treatment Start Date \leq Date < LTFU ART Start Date [a]
 
For AEs leading to treatment withdrawal with start date equal to the LTFU ART Start Date, Intervention Phase instead of Long-term Follow-up Phase will be assigned.

Extension Phase	
Date of Nominal Month 13 Visit \leq Date < LTFU ART Start Date [a]
 
For AEs leading to treatment withdrawal with start date equal to the LTFU ART Start Date, Extension Phase instead of Long-Term Follow-up Phase will be assigned.

Long Term Follow-Up	
For subjects who receive at least one CAB/RPV injection and permanently discontinue study treatment: AE Start Date \geq LTFU ART Start Date
 
AEs with completely missing start date:
 
 • If AE end date is \leq Intervention Phase Treatment Start Date, then assign to Screening Phase; • Else if AE end date is completely missing or Intervention Phase Treatment Start Date $<$ AE end date \leq Date of Nominal Month 13 Visit, then assign to Intervention Phase; • Else if AE end date $>$ Date of Nominal Month 13 Visit, then assign to Extension Phase.

Date=AE Start Date

- [a] If participants have missing LFTU ART start date, only the lower bound will be considered in the derivation.

Table 7 Study Phases for Laboratory, PK, ECG, Vital Signs, HIV-1 Associated Conditions, and Protocol Deviation Data

Study Phase	Definition
Screen	Date ≤ Study Treatment Start Date
Intervention	
For subjects continuing into the Extension Phase: Intervention Phase Treatment Start Date < Date < Date of Nominal Month 13 Visit
 
For subjects not continuing into the Extension Phase: Intervention Phase Treatment Start Date < Date ≤ LTFU ART Start Date ^[a]

Extension Phase	For subjects continuing into Extension Phase: Date of Nominal Month 13 Visit ≤ Date ≤ LTFU ART Start Date ^[a]
Long Term Follow-Up	For subjects who receive at least one CAB/RPV injection and permanently discontinue study treatment: Assessment Date > LTFU ART Start Date

- Date = start or assessment date
- [a] If participants have missing LFTU ART start date, only the lower bound will be considered in the derivation.

Study phase of discontinuation will be determined according to Table 8.

Table 8 Study Phases for Study Conclusion/IP Discontinuation

Study Phase	Definition
Intervention Phase	
For IP Discontinuation: Discontinuation Date is not missing, and no assessments collected at any extension phase nominal visits (e.g. Month 13, Month 15, Month 17 etc.).
 
For Study Conclusion: Discontinuation or Completion Date is not missing, and no assessments collected at any extension phase nominal visits (e.g. Month 13, Month 15, Month 17 etc.) and at any LTFU phase nominal visits (e.g. LTFU Month 3, LTFU Month 6, etc.)

Extension Phase	
For IP Discontinuation: Discontinuation Date is not missing, and assessments collected at any extension phase nominal visits (e.g. Month 13, Month 15, Month 17 etc.).
 
For Study Conclusion: Discontinuation or Completion Date is not missing, and assessments collected at any extension phase nominal visits (e.g. Month 13, Month 15, Month 17 etc.) but no assessments collected at any LTFU phase nominal visits (e.g. LTFU Month 3, LTFU Month 6, etc.)

LTFU Phase	
Not applicable for IP Discontinuation.
 
For Study Conclusion: Discontinuation or Completion Date is not missing, and assessments collected at any LTFU phase nominal visits or has taken any LTFU ART medications (e.g. LTFU Month 3, LTFU Month 6, etc.)

- Discontinuation or Completion Date = date of failure to complete study/date of completing study/date of IP discontinuation

Medication use will be classified as prior and concomitant with study treatment according to Table 9, noting that a medication can be assigned as “taken” during more than one study phase.

Table 9 Study Phases for Non-ART Medications/ART Medications

	Definition
Prior	Medication Taken < Intervention Treatment Start Date
Concomitant during Intervention Phase	
For subjects continuing into Extension Phase: Intervention Treatment Start Date^[a] ≤ Medication Taken < Date of Nominal Month 13 Visit
 
For subjects not continuing into Extension Phase^[b]: Intervention Treatment Start Date^[a] ≤ Medication Taken < LTFU ART Start Date

Concomitant during Extension Phase	For subjects continuing into Extension Phase^[b]: Date of Nominal Month 13 Visit ≤ Medication Taken < LTFU ART Start Date
Received during Long-term Follow-up	For subjects who received at least one CAB and/or RPV injection and have started LTFU ART: Medication Taken ≥ LTFU ART Start Date

NOTES:

- Please refer to Appendix 7: Reporting Standards for Missing Data for handling of missing and partial dates for medications. Use the rules in this table if medication date is completely missing.
 - a. The ART medication stopped on start date of Intervention treatment will be considered a prior medication and will not be considered concomitant during the Intervention phase. If the stop date of ART medication is completely missing and this medication is recorded in eCRF as prior, it will be considered a prior medication and will not be considered concomitant during the intervention phase.
 - b. If subjects have missing LFTU ART start date, only the lower bound will be considered in the derivation.

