13.13.4. Study Population Tables

Study Population Tables					
No.	Population	GSK Standard / Example Shell	Title	Programming Notes	Deliverable
Subject Disposition					
1.1.	Safety	ES1	Summary of Subject Disposition for the Subject Conclusion Record	ICH E3, FDAAA, EudraCT	HL, M12, EOS
1.2.	Safety	SD1	Summary of Treatment Status and Reasons for Discontinuation of Study Treatment	ICH E3	M12, EOS
1.3.	Safety	ES4	Summary of Subject Disposition at Each Study Phase	ICH E3 Intervention/Extension phase: status and reason for withdrawal based on date and reason collected in the study treatment discontinuation form. Long term Follow-up: completion/withdrawal based on data collected in the Study Conclusion form.	M12, EOS
1.4.	Safety	ES5	Summary of Reason for Withdrawal at Each Study Phase	FDAAA, EudraCT	HL, M12, EOS
1.5.	Safety	ES11	Summary of Outcome of Adverse Events Which Led to Study Withdrawal/Treatment Discontinuation at Each Study Phase	EudraCT	M12, EOS
1.6.	Screened	ES6	Summary of Screening Status and Reasons for Screen Failure	Journal Requirements	M12, EOS

Study Population Tables					
No.	Population	GSK Standard / Example Shell	Title	Programming Notes	Deliverable
1.7.	Enrolled	NS1	Summary of Number of Subjects by Country and Site ID	EudraCT/Clinical Operations	M12, EOS
1.8.	Screened	NS1	Summary of Number of Subjects by Site Type and Site ID	Replace Country with Site Type Add column for Investigator Name	M12, EOS
Protocol Deviation					
1.9.	Enrolled	DV1	Summary of Important Protocol Deviations	ICH E3	M12, EOS
1.10.	Enrolled	DV1	Summary of Important COVID-19 Related Protocol Deviations	Update the label for the first row to be "ANY IMPORTANT COVID-19 RELATED PROTOCOL DEVIATIONS"	M12, EOS
1.11.	Enrolled	DV1	Summary of Important Non-COVID-19 Protocol Deviations	Update the label for the first row to be "ANY IMPORTANT NON-COVID-19 RELATED PROTOCOL DEVIATIONS"	M12, EOS
1.12.	Enrolled	DV1	Summary of All COVID-19 Protocol Deviations by Site	Update the label for the first row to be "ANY COVID-19 RELATED PROTOCOL DEVIATIONS". Summary for each site and 'Total' across sites.	HL, M12, EOS

Study Population Tables					
No.	Population	GSK Standard / Example Shell	Title	Programming Notes	Deliverable
1.13.	Enrolled	DV1	Summary of All Implementation Protocol Deviations by Site	Update the label for the first row to be "ANY IMPLEMENTATION RELATED PROTOCOL DEVIATIONS" Summary for each site and 'Total' across sites.	HL, M12, EOS
Population Analysed					

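### SAP Table 8: the Study Conclusion rows overlap for a participant who took LTFU ART but had no LTFU visit, and the stated order rule leaves the LTFU ART clause without effect

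*SAP*

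**What the plan says.** All references are to the current SAP (RAP Amendment 1).

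Table 8 in section 13.4.1 has separate rules for IP Discontinuation and for Study Conclusion. For Study Conclusion, with a discontinuation or completion date present:

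- **Intervention row:** no assessments at any extension-phase nominal visit "and at any LTFU phase nominal visits".
- **Extension row:** assessments at an extension-phase nominal visit, "but no assessments collected at any LTFU phase nominal visits".
- **LTFU row:** "assessments collected at any LTFU phase nominal visits or has taken any LTFU ART medications".

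For the other use of the table, the LTFU row reads "Not applicable for IP Discontinuation".

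Near its start, before Table 6, the section states: "Assessments/events are assigned to study phases sequentially, starting from the top of each table".

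Three displays can use the result:

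- **Table 1.3** (disposition by phase). For Intervention/Extension, its programming note specifies "status and reason for withdrawal based on date and reason collected in the study treatment discontinuation form". For long-term follow-up it uses the Study Conclusion form.
- **Table 1.4** (withdrawal reasons by phase; headline, Month 12 and end of study). It names no source form.
- **Listing 1** (study withdrawal reasons). A phase column is to be added.

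**The concern.** The LTFU row has two routes in, a visit or LTFU ART. The two rows above it close off only the visit route, so the definitions are not mutually exclusive. The section's only stated way of choosing between rows puts LTFU last.

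The case is realistic. Under section 13.2.1.3 the follow-up clock starts on the day of the last injection and the first scheduled LTFU visit is Month 3. Someone can start LTFU ART in that interval and then leave the study without an LTFU assessment.

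What is at stake is the phase to which that departure is attributed. Long-term follow-up exists to observe participants after injections stop. A departure from it that is labelled Intervention or Extension makes retention in follow-up look better than it was. No efficacy, adverse event, laboratory or exposure result depends on this label.

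**Working it through.** The SAP gives no figure to reproduce. The check is a full enumeration of the Study Conclusion rules.

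**Inputs (Table 8).** Three yes/no facts about a participant: any extension visit assessment (E), any LTFU visit assessment (V), any LTFU ART (A). The rows are:

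- Intervention: not E and not V
- Extension: E and not V
- LTFU: V or A

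| E | V | A | Rows met | First row from the top |
|---|---|---|---|---|
| no | no | no | Intervention | Intervention |
| no | no | **yes** | **Intervention + LTFU** | **Intervention** |
| no | yes | no | LTFU | LTFU |
| no | yes | yes | LTFU | LTFU |
| yes | no | no | Extension | Extension |
| yes | no | **yes** | **Extension + LTFU** | **Extension** |
| yes | yes | no | LTFU | LTFU |
| yes | yes | yes | LTFU | LTFU |

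**Result.** Six of the eight combinations meet exactly one row. The other two, with LTFU ART and no LTFU visit, meet two. Taking the first row from the top, LTFU is assigned exactly when V is yes. A never changes an assignment, so the ART clause has no effect.

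**IP Discontinuation.** These rules depend on E alone and have no LTFU category, so nothing overlaps.

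**Against the neighbouring tables.** For participants who have been injected and have permanently stopped treatment, Table 6 places adverse events in LTFU from the LTFU ART start date and Table 7 places assessments there after that date. Table 9 classes medications as received in LTFU from that date for injected participants who have started LTFU ART. None of the three needs an LTFU visit. The same person can therefore have adverse events and ART in LTFU and a study conclusion in Intervention or Extension.

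**Effect on the displays**, assuming they take phase from Table 8 as section 13.4.1 directs:

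- Table 1.3, LTFU row: the participant is missing, because this row uses the Study Conclusion form.
- Table 1.3, Intervention/Extension rows: no change, because they use the treatment discontinuation form.
- Listing 1: the phase column shows Intervention or Extension.
- Table 1.4: the reason moves to Intervention or Extension only if the table is built on study conclusion.

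**Size.** If k participants are affected, the LTFU row of Table 1.3 is short by k. If Table 1.4 uses study conclusion, k/115 of the planned 115 patients move phase. The SAP does not give k. As an assumed range only: k = 0, 1, 2, 3 gives 0/115 = 0%, 1/115 = 0.9%, 2/115 = 1.7%, 3/115 = 2.6%.

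**After the fix.** If the Intervention and Extension rows also require not A, each of the eight combinations meets exactly one row, and the two overlapping ones go to LTFU. Testing the LTFU row first gives the same assignments.

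**The case against.** **The order rule may not govern Table 8.** It is worded for assessments and events and follows sentences about Tables 6 and 7. Table 8 has its own lead-in. Table 9, in the same section, lets a medication belong to more than one phase, so a strict first-match rule cannot hold for every table there. A programmer could reasonably give the ART clause effect and assign LTFU. This stands in part: top-down assignment is the literal reading, not the only one. It does not remove the problem, because without the order rule Table 8 has two matching rows and no tie-break.

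**A reader might infer that every early loss from long-term follow-up is misplaced.** The text does not support that. The LTFU schedule in section 13.2.1.3 has a withdrawal visit with its own assessments. A participant who attends it before LTFU Month 3 can meet the LTFU row by the visit route, and then fails the two rows above. Only participants with LTFU ART and no LTFU assessment at all are affected.

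**A reader might also infer that Intervention/Extension withdrawals are inflated in the disposition table.** They are not. Table 1.3 fills those rows from the treatment discontinuation form, and a person who stopped injections is already counted there correctly. Nor are these departures counted as on-treatment: Table 10 provides a post-treatment state within Intervention and Extension, so phase is not treatment state.

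**The cases can still be traced.** Listing 35 shows ART received during long-term follow-up, and Listings 1 and 2 separate study withdrawal from treatment discontinuation. This is true and is a reason for low severity, but it does not correct the summary row or the phase column.

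**Conclusion.** The overlap is certain from the wording of Table 8. For Study Conclusion, a participant with LTFU ART and no LTFU visit assessment of any kind meets two rows. Under the literal order rule the participant goes to Intervention or Extension, the ART clause does nothing, and Table 8 contradicts Tables 6, 7 and 9. Under the narrower reading of the order rule, the phase is undefined.

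The consequence is confined to the LTFU completion/withdrawal row of Table 1.3, the phase column of Listing 1 and, conditionally, Table 1.4. The number affected cannot be derived from the SAP and may be zero. The rule is wrong as written, with low severity.

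**What to change.** In the Study Conclusion definitions of the Intervention and Extension rows of Table 8, add the condition that the participant has not taken any LTFU ART. Alternatively, state under Table 8 that the LTFU row is evaluated first for Study Conclusion. It would also help to say in the programming note for Table 1.4 which form supplies the withdrawal reason and phase.

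The cost is one clause in two cells, or one sentence. LTFU ART is already used to define phases in Tables 6, 7 and 9, so no new data are needed, and no result outside the disposition displays changes.

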13.4.2. Treatment State

Within each study phase (based on assignment of study phase described in Section 13.4.1), only those events/assessments which occur within the ranges shown in Table 10 will be considered ‘on-treatment’ for the given phase. No treatment states will be assigned to medications.

For adverse events, partial AE start date will use imputation as described in 13.7.2.1.

Table 10 Treatment State within Study Phases

Study Phase	State	Definition
Screen	Pre-Treatment	All assessments/events within phase
Intervention/Extension	On-treatment	Date \leq max (Date of Last CAB LA +RPV LA IM Dose + 35, Date of Last Dose of Oral Study Treatment (CAB+RPV or SOC Bridging) +1)
	Post-Treatment	Date $>$ max (Date of Last CAB LA +RPV LA IM Dose + 35, Date of Last Dose of Oral Study Treatment (CAB+RPV or SOC Bridging) +1)
Long Term Follow-Up	Post-Treatment	All assessments/events within phase

NOTES:

- Date = Assessment/Start Date
- a. Treatment State is determined after data has been assigned to the study phases as defined in Section 13.4.1.
- b. Last injection and/or last dose of oral study treatment (CAB+RPV or SOC bridging) are only applied to participants who permanently discontinued the study treatment. The assessments for participants who did not permanently discontinue the study treatment will be considered 'On-treatment'. For participants continuing into extension phase, all data assigned to intervention phase per Section 13.4.1 will be considered 'On-treatment'

13.4.3. Oral Lead-in Period

Certain displays will be produced for data collected or events occurring during the oral-lead-in period as defined in Table 11 and Table 12.

Table 11 Oral Lead-in Period for AEs

Study Period	Date Range
Oral Lead-in	
For participants receiving at least one Injection: Intervention Treatment Start Date \leq Date [a] $<$ Date of First IM Injection
 
For participants withdrawing prior to first Injection: Date \geq Intervention Treatment Start Date
 
Note that the oral lead-in period is only applicable to the participants who received at least one dose of study treatment during the oral lead-in period in the study. Oral lead-in period is within the intervention phase.

[a] AEs with completely missing start date which have been assigned to the Intervention Phase based on Table 6 will not be assigned to the Oral Lead-in Period.

NOTES:

- Date = AE Start date

Table 12 Oral Lead-in Period for Laboratory Data

Period	Date Range
Oral Lead-in	
For participants receiving at least one Injection: Intervention Treatment Start Date $<$ Date \leq Date of First IM Injection
 
For participants withdrawing prior to first Injection: Date $>$ Intervention Treatment Start Date
 
Note that the oral lead-in period is only applicable to the participants who received at least one dose of study treatment during the oral lead-in period in the study. Oral lead-in period is within the intervention phase.

NOTES:

- Date = Date of assessment

13.5. Appendix 5: Data Display Standards & Handling Conventions

13.5.1. Reporting Process

Software	

 The currently supported versions of SAS software will be used. 	
Reporting Area	
HARP Server	us1salx00259
HARP Compound	\ARPROD\GSK1265744\mid209493\primary_01
Analysis Datasets	

 Analysis datasets will be created according to CDISC standards (SDTM IG Version 3.2 & ADaM IG Version 1.1). 	
Generation of RTF Files	

 RTF files will be generated for all reporting efforts described in the RAP. 	

13.5.2. Reporting Standards

General	

 The current GSK Statistical Display Standards in the GSK Standards Library (IDSL) will be applied for reporting, unless otherwise stated (Library Location: https://spope.gsk.com/sites/IDSLLibrary/SitePages/Home.aspx): 
 4.03 to 4.23: General Principles 5.01 to 5.08: Principles Related to Data Listings 6.01 to 6.11: Principles Related to Summary Tables 7.01 to 7.13: Principles Related to Graphics 	
Formats	

 GSK Statistical Display Principles (5.03 & 6.06.3) for decimal places (DP's) will be adopted for reporting of data based on the raw data collected, unless otherwise stated. Numeric data will be reported at the precision collected on the eCRF. The reported precision from non eCRF sources will follow the GSK Standard Statistical Display Principles but may be adjusted to a clinically interpretable number of DP's. 	
Planned and Actual Time	

 Reporting for tables, figures and formal statistical analyses: 
 Planned time relative to dosing will be used in figures, summaries, statistical analyses and calculation of any derived parameters, unless otherwise stated. The impact of any major deviation from the planned assessment times and/or scheduled visit days on the analyses and interpretation of the results will be assessed as appropriate. Reporting for Data Listings: 
 Planned and actual time relative to study drug dosing will be shown in listings (Refer to GSK Standard Statistical Display Principle 5.05.1). Unscheduled or unplanned readings will be presented within the participant's listings. 	

Unscheduled Visits	

 Unscheduled visits will be assigned to an analysis visit using the all-inclusive windows defined in Section 13.3. However, data summaries will only report visits that are planned assessment time points for each parameter (according to the Schedule of Activities in Section 13.2.1). Evaluable assessments at unscheduled visits will be used when categorizing values across visits, such as 'maximum grade during the intervention phase' or 'at any time post-baseline', and for any algorithm that has specific rules for which observation to use (e.g. snapshot algorithm, LOCF or CVF identification). 	
Descriptive Summary Statistics	
Continuous Data	Refer to GSK Standard Statistical Display Principle 6.06.1
Categorical Data	N, n, frequency, %
Graphical Displays	

 Refer to GSK Standard Statistical Display Principles 7.01 to 7.13. 	

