7.1. Secondary Efficacy Analyses

7.1.1. Endpoint / Variables

- Proportion of participants with Plasma HIV-RNA < 50 copies/mL and plasma HIV-1 RNA ≥ 50 c/mL, respectively, over time using the FDA Snapshot Algorithm. See Section 13.9 for Snapshot Algorithm details.

Other secondary efficacy endpoints:

- Proportion of participants with confirmed virologic failure (CVF) over time
- Absolute values and changes from Baseline CD4+ cell count over time

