13.2. Appendix 2: Schedule of Activities

13.2.1. Protocol Defined Schedule of Events

13.2.1.1. Schedule of Activities for Patient Study Participants (CAB LA + RPV LA Monthly Administration)

Procedures	Screening ^a	Intervention Period												WD ^b
		Day 1	Month 1	Month 2	Month 3	Month 4	Month 5	Month 6	Month 7	Month 8	Month 9	Month 10	Month 11 ^c	
Written Informed Consent ^b	X													
Demography	X													
Eligibility Verification	X													
Physical Exam	X													
Medical History	X													
Center for Disease Control and Prevention (CDC) Classification	X													
Randomization for interviews		X												
Rapid Plasma Reagin (RPR)	X													

Procedures	Screening ^a	Intervention Period													WD ^b
		Day 1	Month 1	Month 2	Month 3	Month 4	Month 5	Month 6	Month 7	Month 8	Month 9	Month 10 ^c	Month 11 ^c	Month 12 ^c	
Symptom Directed Physical Exam and Medical Assessment ^d	X	X	X	X		X		X		X		X		X	X
Injection site reaction (ISR) assessment			X	X	X	X	X	X	X	X	X	X	X	X	X
Vital Signs (temperature, blood pressure [BP], heart rate [HR]) ^e	X	X	X	X		X		X		X			X	X	
Weight, Height & body mass index (BMI) ^f	X	X	X					X					X	X	
HIV Associated Conditions, AE and serious adverse event (SAE) Assessments& Con Meds	X	X	X	X		X		X		X		X	X	X	X
12-Lead ECG ^g	X														X

Procedures	Screening ^a	Intervention Period													WD ^b
		Day 1	Month 1	Month 2	Month 3	Month 4	Month 5	Month 6	Month 7	Month 8	Month 9	Month 10	Month 11 ^c	Month 12 ^c	
Clinical and Hematology			X	X		X		X			X			X	X
Pregnancy Testing (U)rine or (S)erum ^b	U	U	U	U	U	U	U	U	U	U	U	U	U	U	U
HIV-1 RNA	X	X	X	X		X		X		X		X		X	X
Plasma sample for storage ^d		X	X	X		X		X		X		X		X	X
CD4+cell counts	X	X	X	X		X		X		X				X	X
Urinalysis	X														X
Glucose	X														
Prothrombin time (PT)/ partial thromboplastin time (PTT)/ international normalized ratio (INR)	X														X
Oral study product dispensation		X													

Procedures	Screening ^a	Intervention Period													WD ^b
		Day 1	Month 1	Month 2	Month 3	Month 4	Month 5	Month 6	Month 7	Month 8	Month 9	Month 10 ^c	Month 11 ^c	Month 12 ^c	
LA study product administration ^k			X ⁿ	X	X	X	X	X	X	X	X	X	X	X	
Participant Visit Reminder Contact	X	X	X	X	X	X	X	X	X	X	X	X	X	X	
Participant Contact Detail Confirmation	X	X	X	X	X	X	X	X	X	X	X	X	X	X	
Record study visit length ^l			X				X						X		
Patient Questionnaire			X			X								X	
Selected Patient Interviews (SSI) ^m		X												X	

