13.3. Appendix 3: Assessment Windows

13.3.1. Definitions of Assessment Windows for Analyses

Laboratory data, vital signs, ECGs, and genotypic/phenotypic data will be assigned to assessment windows according to actual dates rather than the nominal visit labels as recorded on the eCRF or in the laboratory database.

Prior to visit slotting, assessments are first assigned to a study phase (Screening, Intervention Phase, Extension, or Long Term Follow Up) as defined in Section 13.4.1.

According to the protocol, the nominal target study visit date will be based on the first injection, the Month 1 date. For instance, if Month 1 occurred on July 7th, all subsequent visits are expected to occur on the 7th of each month such that subsequent visits will be August 7th, September 7th, October 7th, etc. Since there are not >28 days in each month of the year, if the Month 1 injection occurred on the 29th, 30th, or 31st of the month, then the target study visit date for the remainder of the visits will be the 28th of the month.

The nominal target study visit day is derived as

- **M1 Target Day** = Date of Actual M1 Injection Visit Date – Date of First Oral lead-in Dose + 1, if subject receives M1 injection; else M1 Target Day = 30.
- **Mx Target Day** = Mx Nominal Target Study Visit Date – Date of First Oral lead-in Dose + 1, for x=2,3, ...

Assessment windows will be derived based on the midpoint between two consecutive planned target study visit dates. For the Snapshot efficacy data, the same approach will be used, except for Month 12, which will use a \pm 6-week window around the projected target study visit date at Month 12.

For parameters which are not scheduled to be assessed at visits, the all-inclusive assessment windows will still be used; however, data summaries will only report scheduled visits. Assessments at unscheduled visits will be included in summaries of worst-case values across visit (e.g. during the intervention phase) and in data listings, as well any algorithms that make use of additional data (e.g., Snapshot).

Table 1 Assessment Windows for Screening, Intervention and Extension Phase Data (Excluding HIV-1 RNA and PK data)

Target (Study Day)	Analysis Window		Analysis Timepoint
	Beginning Timepoint	Ending Timepoint	
Day of earliest record	Assessment Study Day ≤ 1		Screening
For subjects discontinuing prior to receiving first injection:			
30	Assessment Study Day = 2	Study Day of Last CAB/RPV Oral Dose+1	Month 1

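### Table 1 has no Month 8 window, so scheduled Month 8 CD4+ counts are slotted to Month 9 and either drop out of the by-visit summaries or appear under the wrong month

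*SAP*

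**What the plan says.** - **Endpoint.** SAP 7.1.1 lists among the other secondary efficacy endpoints: "Absolute values and changes from Baseline CD4+ cell count over time". Tables 2.8 and 2.9 summarise CD4+ and its change from baseline by visit, for both the Month 12 and end-of-study deliveries.
- **Schedule.** In 13.2.1.1 of the amended plan, the CD4+ row carries nine marks ("CD4+cell counts X X X X X X X X X"). By column these are Screening, Day 1, Months 1, 2, 4, 6, 8, 12 and withdrawal. The earlier plan bound behind it has the same row. Month 9 is blank in both.
- **Windows.** Table 1 in 13.3.1 is titled "Assessment Windows for Screening, Intervention and Extension Phase Data (Excluding HIV-1 RNA and PK data", so it covers CD4+. Its rows run Month 1, 2, 4, 6, 9, 12, 15 and onward. The text above it says: "Assessment windows will be derived based on the midpoint between two consecutive planned target study visit dates". It also says that slotting follows the actual date, not the nominal visit label.
- **Reporting rule.** Under Unscheduled Visits, 13.5.2 states: "However, data summaries will only report visits that are planned assessment time points for each parameter", with the Schedule of Activities as the reference. 13.3.1 makes the same restriction for the window tables.

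**The concern.** The windows and the schedule name different months for the same parameter. Because slotting ignores the nominal label, a correctly timed Month 8 CD4+ count cannot be called Month 8. It becomes Month 9, where no CD4+ count is planned, and the reporting rule then removes it.

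The programmer has two choices. Following the text leaves no CD4+ result between Month 6 and Month 12. Printing Month 9 anyway departs from the stated rule and mislabels the data by a month.

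There is a smaller side effect. 13.6.1 keeps the value nearest the window's target, so an unscheduled count near Month 9 would displace the scheduled Month 8 count.

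**Working it through.** The plan gives no figure to reproduce. The check sets the schedule against the windows and then applies the slotting formulas.

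**1. Are the schedule columns read correctly?** The HIV-1 RNA row in the same grid ("HIV-1 RNA X X X X X X X X X X") has ten marks: Screening, Day 1, Months 1, 2, 4, 6, 8, 10, 12 and withdrawal. The post-baseline months are exactly those of Table 2, so the Month 8 column is correctly identified. The CD4+ row has its mark in that column, and its last two marks fall properly on Month 12 and withdrawal.

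**2. Inputs for slotting.**
- Target dates (13.3.1): the same calendar day each month as the Month 1 injection, or the 28th if that injection fell on the 29th to 31st.
- Visit tolerance (schedule footnote on injections): 7 days either side from Month 4. I assume the CD4+ sample is drawn at the injection visit.
- Month 9 window (Table 1): from M6 + floor[(M9 − M6)/2] + 1 to M9 + floor[(M12 − M9)/2].

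**3. General result.**
- M9 − M6 is 89 to 92 days, so the floor term is 44 to 46 and the Month 9 window opens 45 to 47 days after the Month 6 target.
- M8 − M6 is 59 to 62 days, so a Month 8 visit up to 7 days early is at least 59 − 7 = 52 days after the Month 6 target.
- 52 is greater than 47, so the visit always falls after the Month 9 window opens.
- M9 − M8 is at least 28 days, so a visit up to 7 days late is still before the Month 9 target and well inside the window.

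Enumeration agrees. For all 1,461 Month 1 dates from 1 January 2019 to 31 December 2022 (a range assumed for the check) and 15 offsets each, 1,461 × 15 = 21,915 Month 8 dates were slotted. All 21,915 fell in Month 9 and none in Month 6. The window opens 13 to 16 days before the Month 8 target and closes 74 to 77 days after it.

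**4. Example.** Take the plan's own 7 July Month 1 date, with 2019 assumed as the year.
- Targets: Month 6 on 7 December 2019, Month 8 on 7 February 2020, Month 9 on 7 March 2020, Month 12 on 7 June 2020.
- M9 − M6 = 91 and floor(91/2) = 45, so the Month 9 window opens on 22 January 2020.
- M12 − M9 = 92 and 92/2 = 46, so it closes on 22 April 2020.
- The Month 8 visit range, 31 January to 14 February, lies wholly inside.

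**5. Consequence for reporting.** Six post-baseline CD4+ time points are scheduled in the Intervention Phase (Months 1, 2, 4, 6, 8, 12). Table 1 has a matching row for five of them.

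**6. Other Table 1 parameters.**

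| Parameter | Amended plan | Earlier plan |
|---|---|---|
| CD4+ | Month 8 | Month 8 |
| Vital signs | Month 8, but the later marks sit at Months 11 and 12 with none at withdrawal | Month 8 |
| Chemistry and haematology | Month 9, with the Screening and Day 1 marks absent | Month 8 |

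**The case against.** The best defence is that Table 1 may be right for some parameters. In the amended plan the chemistry and haematology row reads Months 1, 2, 4, 6, 9 and 12, which is exactly the Table 1 pattern. That row looks partly broken, but its right-hand end aligns on Month 12 and withdrawal, so it cannot be dismissed. A reader might infer that all laboratory data are lost at Month 8. The documents do not support that, because the two versions disagree for chemistry and haematology.

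The vital-signs row of the amended plan has also slipped by one cell somewhere after Month 6. If the slip came before the Month 8 mark, that row too would read Month 9. The earlier plan reads Month 8, which makes the mismatch likely for vital signs (Table 3.37), but not certain.

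Month 9 is also a real visit, with an injection and an injection-site assessment. It is unplanned only for particular parameters, so it would be wrong to say that values are assigned to a visit that never took place. Table 1 does apply midpoints consistently between its own targets; the fault is that one target does not suit CD4+.

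Finally, the reporting rule was written with unscheduled visits in mind, and a sensible programmer might print Month 9. That turns omission into mislabelling and does not remove the problem.

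None of this touches CD4+, whose row is intact and identical in both versions.

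**Conclusion.** The mismatch is firm for CD4+ and probable for vital signs. It is open for chemistry and haematology. As written, Month 8 CD4+ counts taken within 7 days of target are slotted to Month 9. They then vanish from Tables 2.8 and 2.9 or appear under the wrong month.

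The statement is limited to timely visits. A count at least 14 to 17 days early, depending on the calendar, would go to Month 6, and one after permanent discontinuation could go to Follow-up. The values stay in the listings and in any summary taken across visits.

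A reader might infer that the Month 12 or virological conclusions are at risk. They are not. Month 12 has its own Table 1 row, Snapshot uses Table 2, which does contain a Month 8 window, and confirmed virologic failure rests on HIV-1 RNA. No hypothesis is tested (2.4). The damage is to one intermediate descriptive time point of a named secondary endpoint. It should be corrected before the tables are produced, but it is not critical.

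**What to change.** Reconcile Table 1 with the Schedule of Activities for each parameter, checking the vital-signs, chemistry and haematology rows against the source schedule. For parameters planned at Month 8 (CD4+, and vital signs if confirmed), use:

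- Month 6 ends at M6 + floor[(M8 − M6)/2].
- Month 8 runs from the next day to M8 + floor[(M12 − M8)/2].
- Month 12 starts the day after that.

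Keep the Month 9 window only for parameters confirmed as planned at Month 9. Replacing it throughout would mis-slot chemistry and haematology if they are indeed drawn then.

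In the example above, M8 − M6 = 62 and M12 − M8 = 121, so Month 8 would run from 8 January to 7 April 2020. With these windows all 21,915 enumerated dates fall in Month 8, a planned time point, and would be reported.

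The cost is three rows in one table, or a second short table, plus the matching derivation code. No data collection changes.
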